- Hemagglutination Inhibition (HI) assay against influenza vaccine strains. In case of lack of agglutination for a specific strain using HI assay, immunogenicity for that strain will be assessed as measured by microneutralization (MN) assay;
- MN titers against influenza vaccine strains.

The results of HI and MN will be analyzed as:

- Geometric mean titer (GMT) on Days 1 and 29;
- Geometric mean-fold ratio (GMFR) as increases of the post-vaccination titer over the pre-vaccination titer;
- SCR on Day 29 as the percentage of participants in a group with either:
 - A pre-vaccination titer below the LLOQ for the respective assay and a post-vaccination titer $\geq 4 \times \text{LLOQ}$; or
 - A pre-vaccination titer $\geq \text{LLOQ}$ and a ≥ 4 -fold increase in post-vaccination titer.
- Proportion of participants with HI titer $\geq 1:10, 1:20, 1:40, 1:80, 1:160$ and $1:320$ on Days 1 and 29;
- Proportion of participants with MN titer $\geq 1:10, 1:20, 1:40, 1:80, 1:160$ and $1:320$ on Days 1 and 29.

CONFIDENTIAL

May not be used, divulged, published or otherwise disclosed without written consent of Arcturus Therapeutics, Inc.

Safety assessments:

- All participants will be monitored for 30 minutes after each study injection for any immediate post-vaccination adverse events (AEs) with appropriate medical treatment readily available in case it is needed.
- Solicited local reactions and systemic AEs will be recorded daily within 7 days after each study vaccination:
 - Local reactions: pain, erythema and swelling at the injection site.
 - Systemic AEs: fatigue, headache, myalgia, arthralgia, nausea, dizziness, chills, and fever.

On Day 1, when ARCT-2303 will be co-administered with the influenza vaccine, participants will be instructed to record local reactogenicity for both arms separately.

Specifically, participants in:

Group 1a and 1b will receive: ARCT-2303 on the left arm and influenza vaccine on the right arm

Group 2a and 2b will receive: ARCT-2303 on the left arm and placebo on the right arm

Group 3a and 3b will receive: placebo on the left arm and influenza vaccine on the right arm

- Any unsolicited AEs will be collected within 28 days after each study vaccination (from Day 1 to Day 29 and from Day 29 to Day 57).

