10.3.3 Safety Analyses

The methods for the safety statistical analyses are described in [Table 10](#).

Table 10 Safety Analyses

| Endpoint | Statistical Analysis Methods |
|-----------|---|
| Secondary | 
Reactogenicity (solicited local and systemic AEs):
 
Percentages of participants experiencing each solicited AE will be summarized for each symptom by any (severity), maximum severity (mild, moderate or severe, except fever) during 7 days after vaccination by study arm. For the definition of severity grades, refer to Table 7.Duration and time of onset of events will be summarized by study arm descriptively by mean, SD etc.Injection site erythema and swelling will be summarized according to categories based on linear measurements.Use of antipyretics and analgesics will be summarized by frequency and percentage of participants reporting use.Body temperature will be summarized by 0.5°C increments from 38.0°C up to ≥40°C. In addition, fever will be summarized according to “mild”, “moderate” or “severe” categorization. 
Unsolicited AEs, SAEs, MAAEs, and AESIs:
 
Percentages of participants reporting at least one AE, related AE, SAE, MAAE, AESI within 28 days after each study vaccination will be summarized by study arm.Percentages of participants reporting at least one SAE, MAAE, AESI.Percentages of participant withdrawal/early termination from the study will be summarized by study arm.Percentages of participants reporting any AEs within 30 minutes after each study vaccination will be summarized by study group. 
AEs will be coded using the most recent version of MedDRA. AEs will be presented by SOC and PT by study group.
 
Data listings of all AEs will be provided by participant at final analysis.
 
All safety analyses will be performed on the SAF. Missing data will not be imputed.
 |

Abbreviations: AE, adverse event; AESI, adverse event of special interest; MAAE, medically attended adverse event; MedDRA, Medical Dictionary for Regulatory Activities; PT, preferred term; SAE, serious adverse event; SAF, safety analysis set; SD, standard deviation; SOC, system organ class.

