## 7.2 Unsolicited Adverse Events

All unsolicited AEs including SAEs, MAAEs and AESIs will be coded using MedDRA. Medical occurrences that begin before the study vaccination but after obtaining informed consent will be recorded in the medical history/current medical conditions section of the eCRF, not the AE section, all unsolicited AEs collected on the AE CRF page following the first administration will be considered TEAEs and will be included in the summaries.

Summary tables will include the number of participants (%) experiencing an event along with the number of events. Participants will be counted only once for each SOC and PT level (categorical descriptive analysis). All TEAE summaries will be presented by study group, SOC and PT.

The TEAE summaries will include:

- Overview summary of unsolicited AEs (Day 1 – Day 57)
- Summary of unsolicited AEs reported within 30 minutes after each study vaccination (derived by onset date time if event after vaccination date time) by SOC and PT. Please note that for Day 1, when 2 vaccinations are given, the 30 minutes interval is from the second vaccination.
- Summary of unsolicited AE within 28 days after each study vaccination by SOC and PT.
- Summary of related unsolicited AEs within 28 days after each study vaccination by SOC and PT
- Summary of unsolicited AE within 28 days after each study vaccination by SOC, PT and severity.
- Summary of related unsolicited AEs within 28 days after each study vaccination by SOC, PT and severity
- Summary of SAEs by SOC and PT
- Summary of related SAEs by SOC and PT
- Summary of SAEs by SOC, PT and severity
- Summary of related SAEs by SOC, PT and severity
- Summary of MAAEs by SOC and PT
- Summary of related MAAEs by SOC and PT
- Summary of AESIs by SOC and PT
- Summary of related AESIs by SOC and PT
- Summary of AEs leading to discontinuation from study by SOC and PT
- Summary of related AEs leading to discontinuation from study by SOC and PT
- Summary of (S)AEs with fatal outcome by SOC and PT

Additionally, the following summaries up to 28 days post Day 1 vaccination will be provided for Groups 2a and 2b combined (ARCT-2303), Groups 3a and 3b combined (QIV/aQIV):

- Summary of unsolicited AEs by SOC and PT
- Summary of related unsolicited AEs by SOC and PT
- Summary of SAEs by SOC and PT

For final analysis, summary of SAEs, MAAEs, AESI, AE leading to discontinuation and death will be presented cumulatively (Day 1 to EOS).

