## **9 CHANGES TO THE PLANNED ANALYSIS**

Not applicable.

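### SAP 7.2 lists no 28-day, by-vaccination percentages for MAAEs or AESIs, and only part of them for SAEs, although protocol Table 10 plans all three; SAP Section 9 declares no change

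*SAP*

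**What the plan says.** Protocol 10.3.3, Table 10, has two lines for these events. The first covers participants with "at least one AE, related AE, SAE, MAAE, AESI within 28 days after each study vaccination will be summarized by study arm". The second reads "Percentages of participants reporting at least one SAE, MAAE, AESI" and states no window. The synopsis gives the two windows when it describes unsolicited event collection: "within 28 days after each study vaccination (from Day 1 to Day 29 and from Day 29 to Day 57".

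SAP 7.2 applies the 28-day window after each vaccination to unsolicited AEs and related unsolicited AEs, each also by severity. The MAAE and AESI tables are listed as "Summary of MAAEs by SOC and PT" and "Summary of AESIs by SOC and PT", each with a related-event counterpart and no window. Four SAE tables by study group are also listed without a window. SAP 7.2 then says: "Additionally, the following summaries up to 28 days post Day 1 vaccination will be provided for Groups 2a and 2b combined (ARCT-2303", with Groups 3a and 3b as the second pooled column. That set has an SAE table but no MAAE or AESI table. On the second analysis it says: "For final analysis, summary of SAEs, MAAEs, AESI, AE leading to discontinuation and death will be presented cumulatively (Day 1 to EOS". SAP Section 1 gives Day 1 to Day 57 as the span for these events at the first analysis.

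SAP Section 9, on changes to the planned analysis, says "Not applicable".

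**The concern.** The unwindowed line in Table 10 stands beside the 28-day line and does not replace it. A programmer working from SAP 7.2 would produce the unwindowed tables and have no instruction to produce the windowed MAAE and AESI percentages.

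The window matters because of the crossover. Groups 3a/3b receive an influenza vaccine and placebo on Day 1 and ARCT-2303 on Day 29 (SAP 2.1). Day 1 to Day 29 is therefore the only period with a randomised group not yet exposed to ARCT-2303. Groups 2a/2b make the opposite move, so by Day 57 the Group 2 and Group 3 columns hold the same products in reverse order. A table that runs across Day 29 cannot show which vaccination an event followed.

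The windowed SAE table does not fill the gap. Protocol 9.1.15 defines MAAEs as events that are not serious, and AESIs may be nonserious (protocol 9.1.7).

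**Working it through.** **Step 1. Carry-over of the Table 10 28-day line into SAP 7.2.** The plan has no figure to reproduce here; the check is a line-by-line comparison.

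| Item in Table 10 | 28-day table after each vaccination in SAP 7.2 |
|---|---|
| AE | Yes, by study group |
| Related AE | Yes, by study group |
| SAE | In part: post-Day 1 only, pooled 2a+2b and 3a+3b; none for 1a/1b, none after Day 29 |
| MAAE | None listed |
| AESI | None listed |

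The SAP document history records the addition of the pooled post-Day 1 summaries in version 3.0, but no decision to drop the MAAE or AESI percentages.

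**Step 2. What the listed spans cover for Groups 3a/3b.** Planned size is 400 + 160 = 560 of 1680 participants (one third). On nominal study days:

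- To Day 57: (57 − 29)/(57 − 1) = 28/56 = 50% of the time follows ARCT-2303.
- To end of study: (181 − 29)/(181 − 1) = 152/180 = 84%.

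SAP 10.2 also describes the second analysis as covering data from Day 57 onward. If that yields a separate summary, it lies wholly after the switch.

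**Step 3. Illustration of dilution.** The documents give no MAAE or AESI rates, so every rate here is an assumption:

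- b = background MAAE risk per 28 days, 2% to 5%
- e = excess in the 28 days after ARCT-2303 given on Day 1, 1 to 4 points
- r = Day 29 excess divided by Day 1 excess
- f = share of Group 3 given the Day 29 dose; 90% borrows the 10% dropout in protocol 10.2
- no influenza-vaccine effect, and undosed participants stay under observation at background risk

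Day 1 to Day 29: Group 2 has b + e and Group 3 has b, so the full excess shows. For 560 participants that is 560 × 0.01 = 5.6 to 560 × 0.04 = 22.4 people.

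To Day 57:

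- Group 2: 1 − (1 − b − e)(1 − b)
- Group 3: 1 − (1 − b)(1 − b − f·r·e)
- Difference: e(1 − b)(1 − f·r)

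To end of study the difference is e(1 − b)^(152/28)(1 − f·r).

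Share of e still visible, for b = 2% / b = 5%:

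| f, r | To Day 57 | To end of study |
|---|---|---|
| 1, 1 | 0% / 0% | 0% / 0% |
| 0.9, 1 | 9.8% / 9.5% | 9.0% / 7.6% |
| 1, 0.5 | 49.0% / 47.5% | 44.8% / 37.8% |
| 0.9, 0.5 | 53.9% / 52.3% | 49.3% / 41.6% |

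Example with b = 5%, e = 4 points: before the switch, 9.0% vs 5.0%. To Day 57, Group 2 has 1 − 0.91 × 0.95 = 13.55%. Group 3 has 1 − 0.95 × 0.914 = 13.17% with f = 0.9, r = 1, or 1 − 0.95 × 0.93 = 11.65% with f = 1, r = 0.5.

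**The case against.** The best answer for the plan is the overview table of unsolicited events that opens the SAP 7.2 list. An overview is the natural home for rows counting participants with one or more events of a type, and SAP 7.2 treats SAEs, MAAEs and AESIs as unsolicited AEs. The list is not stated to be exhaustive either. This stands in part: the overview may well have such rows. But its content is not specified, and its stated span is Day 1 to Day 57 with no split by vaccination, so it does not commit to the Table 10 percentages.

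Second, the stated safety endpoint is met. Protocol Table 4 and SAP 2.2.2 attach the 28-day window to unsolicited AEs and define SAEs, MAAEs and AESIs over the whole study. SAP 7.2 follows that split. This stands in full. What goes unplanned is one descriptive line of Table 10, not an endpoint.

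Third, a reader might infer that the SAP plans a pooled MAAE or AESI comparison to Day 57 or end of study. It does not. The pooled summaries in SAP 7.2 stop 28 days after Day 1, and SAP 3.9 concerns subgroups for selected parameters without naming MAAEs or AESIs. Dilution arises only when a reader sets the listed Group 2 and Group 3 columns side by side.

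Fourth, safety monitoring does not rest on these tables. An unblinded DSMB reviews cumulative data, SAEs and AESIs are reported within 24 hours, and suspected myocarditis or pericarditis is adjudicated. That is correct and limits the consequence, but it does not supply the planned percentages.

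**Conclusion.** The mismatch is established from the text: the by-vaccination 28-day percentages are not listed for MAAEs or AESIs, are listed only in part for SAEs, and no change is declared. It is a minor to should-fix point.

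Three stronger readings are not supported. It would be wrong to say that the pooled table is all the SAP gives for SAEs, because by-group SAE tables without a window are also listed. Nor are the events lost: those with onset in the windows are counted in the 28-day SOC and PT tables, though not marked as MAAEs or AESIs there, and they appear in the end-of-study listings. Nor does the illustration predict a result. It rests wholly on assumed rates, covers MAAEs only, and full cancellation is its extreme case, needing an equal excess at both doses and everyone dosed on Day 29.

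What rests on the plan alone is the mixing of exposure in the Group 3a/3b columns, 50% of the time to Day 57 and 84% to end of study on nominal days. Safety is descriptive (protocol 10.1), so no test, alpha or power depends on this.

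**What to change.** In SAP 7.2:

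1. Add the percentages of participants with at least one SAE, MAAE and AESI in the 28 days after the Day 1 vaccination and, separately, after the Day 29 vaccination, for all six groups. Rows in an overview table split by vaccination would do.
2. Add MAAEs and AESIs to the existing pooled post-Day 1 summaries for Groups 2a+2b and 3a+3b.
3. Keep the cumulative tables, which the whole-study endpoint needs, with a footnote that Groups 3a/3b received ARCT-2303 on Day 29.

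If any Table 10 summary is left out on purpose, say so in SAP Section 9.

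The cost is SAP wording and a few extra descriptive tables, built from onset and vaccination dates already collected.

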Individuals will be randomly assigned to one of the three study groups:

- Group 1a (ARCT-2303/Flucelvax Quadrivalent, N=400): participants will receive one dose of ARCT-2303 and one dose of Flucelvax Quadrivalent (opposite arms) on Day 1, and one dose of placebo on Day 29.
- Group 2a (ARCT-2303, N=400): participants will receive one dose of ARCT-2303 and one dose of placebo (opposite arms) on Day 1, and one dose of Flucelvax Quadrivalent on Day 29.
- Group 3a (Flucelvax Quadrivalent, N=400): participants will receive one dose of Flucelvax Quadrivalent and one dose of placebo (opposite arms) on Day 1, and one dose of ARCT-2303 on Day 29.

Cohort B (participants ≥ 65 years of age; approximately 480 participants)

Individuals will be randomly assigned to one of the three study groups:

- Group 1b (ARCT-2303/Fluad Quadrivalent, N=160): participants will receive one dose of ARCT-2303 and one dose of Fluad Quadrivalent (opposite arms) on Day 1, and one dose of placebo on Day 29.
- Group 2b (ARCT-2303, N=160): participants will receive one dose of ARCT-2303 and one dose of placebo (opposite arms) on Day 1, and one dose of Fluad Quadrivalent on Day 29.
- Group 3b (Fluad Quadrivalent, N=160): participants will receive one dose of Fluad Quadrivalent and one dose of placebo (opposite arms) on Day 1, and one dose of ARCT-2303 on Day 29.

In addition, all available serum samples from study participants of study ARCT-154-J01 who received a booster dose of candidate ARCT-154 vaccine according to the protocol, provided pre- and post-vaccination blood samples, and did not have evidence of SARS-CoV-2 infection and major protocol deviations, will be selected to use as a comparator. This set of samples will compose up to 385 individuals 18 years of age and above, who were included in the Per Protocol Set 1 (PPS-1). These samples will be tested in this study for assessment of coprimary study objectives 1 and 2.

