1.2 Schedule of Assessments

The schedule of assessments (SoA) for ARCT-2303-01 is shown in [Table 1](#).

Table 1 Schedule of Assessments

| Visit Type: | Screening and Vacc1 | Follow-up Visit 1 and Vacc2 | Follow-up Visit 2 | Safety call | Final Visit (EOS) | Unscheduled Visit | Early Termination (ET) Visit |
|---|----------------------|-----------------------------|---------------------|-------------|---------------------|------------------------|------------------------------|
| | Clinic ^a | Clinic ^a | Clinic ^a | TC | Clinic ^a | Clinic ^{a, c} | Clinic ^a |
| Study Day: | 1^b | 29 | 57 | 91 | 181 | N/A | N/A |
| Visit Window (days): | -7 | ±3 | ±3 | ±7 | ±7 | N/A | N/A |
| Informed consent | X ^b | | | | | | |
| Weight/height | X ^b | | | | | | |
| Medical history and demographics | X ^b | | | | | | |
| Physical examination ^d | X ^b | X | X | | X | X | X |
| Vital signs, and body temperature ^e | X ^b | X | X | | X | X | X |
| Pregnancy test ^f | X ^b | X | | | | | |
| Testing for COVID-19 ^g | X ^b | X | | | | X ^g | |
| Review of inclusion/exclusion criteria | X ^b | | | | | | |
| Contraindication for second vaccination ^h | | X | | | | | |
| Randomization | X | | | | | | |
| Blood sampling for immunogenicity and safety testing ⁱ | X | X | | | X | (X) | (X) |
| 12-lead electrocardiogram ^j | X | | | | | X | |
| Study vaccine administration ^k | X | X | | | | | |
| Post-vaccination observation ^{e, l} | X | X | | | | | |
| Dispense eDiary and training | X | | | | | | |
| Diary compliance check ^m | X | X | X | | | | |
| Adverse events ⁿ | X ^b | X | X | X | X | X | X |
| Concomitant medication/vaccines collection | X ^b | X | X | X | X | X | X |

Abbreviations: AE, adverse event; AESI, adverse event of special interest; COVID-19, coronavirus disease 2019; ECG, electrocardiogram; eDiary, electronic diary; ET, early termination; MAAE, medically attended adverse event; N/A, not applicable; RT-PCR, real-time polymerase chain reaction; SAE, serious adverse event; SARS-CoV-2, severe acute respiratory syndrome coronavirus 2; TC, telephone call; Vacc, vaccination.

a Visits will be performed in person unless the participant is otherwise directed to be seen at a hospital or to remain at home (if telemedicine/telephone visits are the only feasible option).

CONFIDENTIAL

May not be used, divulged, published or otherwise disclosed without written consent of Arcturus Therapeutics, Inc.

Table 1 Schedule of Assessments

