5.3 Contraindications for the Second Vaccination

The following events constitute absolute contraindications to further administration of study vaccines.

If any of these events occur during the study, the participant must not receive additional doses of vaccine, but should be encouraged to continue study participation for safety at the discretion of the investigator:

- Anaphylaxis or systemic hypersensitivity reaction following the administration of vaccine.
- Any SAE judged to be related to study vaccination.
- Pregnancy.
- Any adverse event that, in the opinion of the investigator, poses an additional risk to the participant if he/she continues to participate in the study.

The following events constitute contraindications to administration of study vaccine at certain points in time, and if any of these events occur at the time scheduled for vaccination, the participant may be vaccinated at a later date, preferably within the time window specified in the protocol (Table 1), or the participant may be withdrawn at the discretion of the investigator:

- Any COVID-19 that occurred after Visit 1 or a positive result of COVID-19 test pre-vaccination.
- Acute moderate or severe infection with or without fever at the time of vaccination.
- Fever, defined as temperature $\geq 38.0^{\circ}\text{C}$ (100.4°F ; measured by any method) at the time of vaccination.

Participants with a minor illness without fever, as assessed by the investigator, can be administered study vaccines.

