- **Repeat/unscheduled assessments**: Only values collected at scheduled study visits/time points will be presented in summary tables. If a repeat assessment was performed, the result from the original assessment will be presented as the result at the specific visit/time point (early termination visits will not be summarized). All collected data will be included in the data listings.
- **Duplicate entries in eDiary**: For duplicate daily entries in the electronic diary with at least one different value collected between 2 entries, the last data entered will be considered for the analysis (rule established before any planned analysis).
- **Assessment windows**: All assessments will be included in the data listings and no visit windows will be applied to exclude assessments that were performed outside of the protocol specified procedure windows. For safety summaries (where applicable), the table below defines the analysis time windows that correspond to the targeted visit.

Visit (target day)	Visit window (days)
Study Day 1: Screening and Vaccination 1	-7
Study Day 29: Follow-up Visit 1 and Vaccination 2	± 3
Study Day 57: Follow-up Visit 2	± 3
Study Day 91: Safety Call	± 7
Study Day 181: Final Visit (EOS)	± 7

- Result display convention: Results will be center aligned in all summary tables and listings. Participant identifiers visit and parameter labels may be left-aligned if required.
- Date and time display conventions: The following display conventions will be applied in all outputs where dates and/or times are displayed:

Date only: YYYY-MM-DD

Date and time: YYYY-MM-DD HH:MM

If only partial information is available, unknown components of the date or time will be presented as 'NK' (not known), i.e., '2016-NK-NK'. Times will be reported in military time.

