### 3.2 Key Definitions

The following definitions will be used:

- Baseline: The baseline value is defined as the last available valid (quantifiable continuous or categorical value), non-missing observation for each participant prior to first study vaccine administration. If an assessment is taken on the day of first study vaccine administration, but the time is not available, this assessment will be considered for baseline assessment. Repeat and unscheduled assessments will be included in the derivation of the baseline values.
- Change from Baseline: The change from baseline value is defined as the difference between the result collected/derived at a post-baseline visit/time point and the baseline value.

The change from baseline value at each post-baseline visit/time point will be calculated for all continuous parameters using the following formula:

$$\text{Change from Baseline Value} = \text{Result at Visit/Time Point} - \text{Baseline Value}$$

The change from baseline value will only be calculated if the specific post-baseline visit/time point result and the baseline value for the parameter are both available and will be treated as missing otherwise.

- Study day: The study day of an event is defined as the relative day of the event starting with the date of the first study vaccine administration (reference date) as Day 1 (there will be no Day 0).

The study day of events occurring before the first study vaccine administration will be calculated as:

$$\text{Study Day} = (\text{Date of Event} - \text{Date of First Study Vaccine Administration})$$

For events occurring on or after Day 1, study day will be calculated as:

$$\text{Study Day} = (\text{Date of Event} - \text{Date of First Study Vaccine Administration}) + 1$$

Study days will only be calculated for events with complete dates and will be undefined for events that are 'Ongoing' at the time of database lock (either Day 57 or end of study).

Relative days compared to an alternative reference point will be calculated similarly, but the alternative starting reference start date will be used instead of the date of the first study vaccine dosing.

- Prior Medications: Prior medications are defined as any medication stopped prior to the first administration of the study vaccine.

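### SAP 7.2 does not end the post-Day 1 window for unsolicited AEs and SAEs at the second injection, so events after the switchover dose can be tabulated under the Day 1 vaccine

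*SAP*

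**What the plan says.** SAP 7.2 (Unsolicited Adverse Events) plans two kinds of time-limited table. The first kind covers the 28 days after each injection, by group. The second kind pools groups: "the following summaries up to 28 days post Day 1 vaccination will be provided for Groups 2a and 2b combined (ARCT-2303"), with Groups 3a and 3b pooled in the same way as QIV/aQIV. The pooled set covers unsolicited AEs, related unsolicited AEs and SAEs. The SAP document history records it as an addition in Amendment 2.0.

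On timing, SAP 3.2 defines study day as the "relative day of the event starting with the date of the first study vaccine administration (reference date) as Day 1", with no Day 0. SAP 3.1 lists "Study Day 29: Follow-up Visit 1 and Vaccination 2" with a window of ±3 days, matching Table 1 of the protocol ("Visit Window (days): | -7 | ±3 | ±3 | ±7 | ±7"). The protocol synopsis gives the unsolicited collection periods as "from Day 1 to Day 29 and from Day 29 to Day 57".

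On what the second injection contains, the synopsis wording for Group 3a, which goes on to give the day number as 29, is "participants will receive one dose of Flucelvax Quadrivalent and one dose of placebo (opposite arms) on Day 1, and one dose of ARCT-2303 on Day". Group 3b follows the same pattern with the adjuvanted influenza vaccine first. Groups 2a and 2b receive ARCT-2303 first and influenza vaccine at the second visit.

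**The concern.** Before the switchover, Group 3 is the only group that has not received ARCT-2303. From the second visit on, every group is due to have had it. The post-Day 1 tables are therefore the only unsolicited AE and SAE tables in which ARCT-2303 can be set beside a column free of it.

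If the first window runs past the second injection, that separation fails in both directions. The days at risk are the injection day and those just after it. Protocol Table 2 notes that vaccine-related allergic symptoms typically begin within a few minutes. Anaphylaxis is not on the solicited list, so it would be handled as an unsolicited event. With rare SAEs, one event in the wrong column can change how the table reads. The first final analysis produces no individual listings (SAP 10.1), so a reader of the initial study report could not trace the event.

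**Working it through.** **Inputs**
- Study day = date − date of first vaccination + 1 (SAP 3.2).
- First window: up to 28 days after the Day 1 vaccination (SAP 7.2).
- Second injection: Day 29 ± 3, that is Day 26 to Day 32 (SAP 3.1; Protocol Table 1).
- Pooled group sizes: 400 + 160 = 560 planned for Groups 2a and 2b, and 400 + 160 = 560 for Groups 3a and 3b.

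**The plan's own figure.** First vaccination + 28 days gives Study Day 28 + 1 = 29. This agrees with the synopsis, whose first collection period runs from Day 1 to Day 29. The second period also starts on Day 29, so that day belongs to both.

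**Overlap.** Let v be the study day of the second injection. The calendar days of the first window that fall on or after the injection day are max(0, 29 − v + 1) if the window is Days 1-29, and max(0, 28 − v + 1) if it is read as Days 1-28.

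| Second injection on | Window Days 1-29 | Window Days 1-28 |
|---|---|---|
| Day 26 | 4 | 3 |
| Day 27 | 3 | 2 |
| Day 28 | 2 | 1 |
| Day 29 | 1 | 0 |
| Days 30-32 | 0 | 0 |

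Under the first reading the overlap runs from 1/29 = 3.4% of the window (Day 29) to 4/29 = 13.8% (Day 26).

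**Illustration only.** The documents do not give the distribution of visit days. If visits were spread evenly over Days 26-32, then under the Days 1-29 reading 4/7 = 57% of participants would have some overlap, with a mean of (4 + 3 + 2 + 1)/7 = 10/7 = 1.4 days. Under the Days 1-28 reading the figures are 3/7 = 43% and 6/7 = 0.9 days. If every visit fell exactly on Day 29, everyone would overlap by one day under the first reading and nobody under the second.

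**Is the gap closed elsewhere?** I found no rule that does so.
- SAP 3.2 defines treatment emergence relative to the first administration only.
- SAP 3.8 gives one treatment label per group, not one per period.
- SAP 7.2 compares onset date-time with vaccination date-time only for the 30-minute table.

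**After the change.** If the first window ends at the earlier of 28 days or the second injection, the overlap is 0 for every v from 26 to 32.

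**The case against.** The strongest reply is that silence is not an instruction. The SAP nowhere directs that post-switchover events be counted under the Day 1 product, and the synopsis describes two successive periods that a programmer could sensibly split at the Day 29 visit. That stands, and a reader should not infer that the SAP prescribes misattribution. But the synopsis wording leaves Day 29 in both periods and says nothing about a visit on Days 26-28. Two competent programmers could produce different columns.

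A second reply is that 28 days might mean Days 1-28, since the eDiary count in Protocol 8.12.3 starts on the day of vaccination. On that reading an on-schedule visit gives no overlap. This also stands, but early visits still overlap by 1 to 3 days.

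Third, an immediate event is not lost. It should appear in the 30-minute table and the post-Day 29 table, and in the listings at the second analysis. That is true. What remains is an additional, wrongly labelled count in the post-Day 1 tables.

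Fourth, the common reactions are out of reach. Pain, fever, fatigue and the other solicited terms are tabulated for 7 days after each vaccination (SAP 7.1), and a window that follows Day 1 by 7 days cannot reach Day 26. That stands in full, so the point is confined to unsolicited AEs and SAEs.

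Finally, Protocol 10.1 plans no formal safety test, so no primary or secondary hypothesis depends on these tables. That also stands.

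**Conclusion.** The gap is real and bounded. As worded, the post-Day 1 tables can include unsolicited AEs and SAEs with onset after the switchover dose: ARCT-2303 events under QIV/aQIV in Groups 3a and 3b, and influenza vaccine events under ARCT-2303 in Groups 2a and 2b. The overlap is at most 4 calendar days per participant and is zero when the second injection is on Day 30 or later. Protocol 5.3 allows delay ("the participant may be vaccinated at a later date, preferably within the time window specified in the protocol"), and delayed doses add no overlap. In the tables by injection, the same event could be counted under both injections.

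Two stronger inferences are not supported. One is that all 560 participants in each pooled group are affected. That is the population at risk, and how many overlap depends on visit days the documents do not give. The other is that the error pulls the two columns together. Stray events would be added to both columns, and the direction of the net change depends on event rates after each second dose, which are also not given. The number of misassigned events cannot be computed from the documents.

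**What to change.** Add to SAP 7.2:
- The post-Day 1 window ends at the earlier of 28 days after the Day 1 vaccination or the date-time of the second-visit injection.
- The second window starts at that injection.
- Each AE onset is assigned to one window only.
- A stated rule covers an onset on the injection date with a missing time.

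Apply this to the tables by injection and to the pooled Group 2 and Group 3 tables. The text should also say where an onset on Day 30 or 31 is shown when the second injection is on Day 31 or 32, because such an event falls in neither 28-day window.

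The cost is a SAP revision and one programming condition. Administration date and time are already captured (SAP 5.6), and onset date-time is already used for the 30-minute table. No protocol amendment, new data or additional participants are needed.
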